5.2 Trial Treatments

The treatment to be used in this trial is outlined below in Table 2.

Patients will be treated with the combination of azacitidine and MK3475. The dose of azacitidine will be 75 milligrams per meter squared IV or SC daily for 7 consecutive days following a standard administration guidelines for this compound. MK3475 will be administered at a dose of 200 milligrams every three weeks starting on Cycle 1 Day 1 and will continue every three weeks thereafter independent of azacitidine dosing. A cycle will be considered as 4 weeks and will be based upon the azacitidine dosing schedule. Cycles will be repeated for as long as possible unless evidence of significant toxicity or progression to AML (defined by more than 30% blasts in the marrow), unless there is frank proliferation in peripheral blood (in the opinion of the treating physician), or if it is not safe for the patient. Patients will receive the first course of therapy without interruption regardless of the degree of myelosuppression. Patients can continue to receive therapy indefinitely until one of the criteria outlined below occurs. After the first course of therapy the interval between cycles of therapy can be spaced out at the discretion of the treating physician, but will otherwise be scheduled as close to possible to the initial 4 weeks. If there is evidence of prolonged myelosuppression defined by absolute neutrophil count of less than $1 \times 10^9/\text{dl}$ and a platelet count of less than $30 \times 10^9/\text{dL}$ for more than 42 days with evidence of hypocellular marrow (defined as marrow cellularity of less than 5%), subsequent courses of the azacitidine will be given at the next lower dose after the counts have recovered to an ANC of more than $1 \times 10^9/\text{dL}$ and platelet more than $30 \times 10^9/\text{dL}$. Cycles will be repeated as long as possible until toxicity or lack of response for at least 6 cycles of combination therapy.

In the absence of treatment delays due to early trial termination as described in Section 5.10, treatment may continue indefinitely until one of the following criteria applies:

Product: Pembrolizumab

20

Protocol/Amendment No.: 2016-0343 Amendment 3.4

1-Clinically significant progressive disease

2-Possibility of undergoing allogeneic stem cell transplant

3-Clinical significant intercurrent illness that prevents further administration of treatment

4-Patient request or general or specific changes in the patient condition that render the patient unacceptable for further treatment in the judgment of the investigator or treating physician

Product: Pembrolizumab

Protocol/Amendment No.: 2016-0343 Amendment 3.4

Table 2. Trial Treatment

Drug	Dose/Potency	Dose Frequency	Route of Administration	Regimen/Treatment Period	Use
Pembrolizumab	200 mg	Q3W	IV infusion	Starting on day 1 of initial treatment and every 3 weeks thereafter	Experimental
Azacitidine	75 mg/m ²	Q4W	IV or SC infusion	Day 1 to 7 of each 4 week cycle	Standard

Please note that in this schedule, pembrolizumab and azacitidine run as to parallel treatment schedules.

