4.0 BACKGROUND & RATIONALE

4.1 Myelodysplastic syndromes (MDS)

The myelodysplastic syndromes (MDS) are a group of heterogeneous malignancies that manifest clinically by peripheral cytopenias and an increase risk of transformation to acute myelogenous leukemia (AML). Patients with MDS are in general divided into those with lower risk disease and those with higher risk disease. The standard of care for most patients with high risk MDS is a hypomethylating agent such as azacitidine (1, 2). Data from the now classic aza-001 trial (1) suggest that hypomethylating agents are associated with improved survival compared to supportive care. Longer follow up and experience with these compounds indicates that a large majority of the patients treated with these agents will eventually lose response to the hypomethylating agents. This phenomenon is called hypomethylating failure. The survival of such patients is very poor estimated to be 4 to 6 months (3, 4). Therefore the need for new agents or combinations in patients with MDS both as front line (to improve survival and delay failure) and in patients with HMA failure to improve survival. It should be noted that at this moment there are no drugs approved for HMA failure MDS (2).

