Drug interaction studies with 5-azacitidine have not been conducted. An in vitro study of 5-azacitidine incubation in human liver fractions indicated that azacitidine may be metabolized by the liver. Whether azacitidine metabolism may be affected by known microsomal enzyme inhibitors or inducers has not been studied. The potential of azacitidine to inhibit cytochrome P450 (CYP) enzymes is not known. In vitro studies with human cultured hepatocytes indicate that azacitidine at concentrations of 1.0 μ M to 100 μ M does not induce CYP 1A2, 2C19, or 3A4/5. Hydroxurea is known to inhibit ribonuclease reductase, a key enzyme required for the incorporation of 5-azacytidine residues into DNA. Therefore, hydroxyurea may potentially limit the clinical activity of 5-azacytidine and its use during this clinical trial should be avoided.

Route of Administration: Intravenous

Preparation: Azacitidine is a cytotoxic drug and, as with other potentially toxic compounds, caution should be exercised when handling and preparing suspensions. If reconstituted azacitidine comes into contact with the skin, immediately and thoroughly wash with soap and water. If it comes into contact with mucous membranes, flush thoroughly with water.

How Supplied: Azacitidine is supplied as 100 mg vials of lyophilized powder.

Product: MK-3475

63

Protocol/Amendment No.: 2016-0343 Amendment 2

Storage: Store un-reconstituted vials at 25° C (77° F); excursions permitted to 15°-30° C (59°-86° F) (See USP Controlled Room Temperature). There is no need to protect azacitidine from exposure to light.

Handling and Disposal: Procedures for proper handling and disposal of anticancer drugs should be applied.

Reported Adverse Events and Potential Risks:

In clinical studies, the most commonly occurring adverse reactions were nausea (70.5%), anemia (69.5%), thrombocytopenia (65.5%), vomiting (54.1%), pyrexia (51.8%), leucopenia (48.2%), diarrhea (36.4%), fatigue (35.9%), injection site erythema (35.0%), constipation (33.6%), neutropenia (32.3%), and ecchymosis (30.5%). Other adverse reactions included dizziness (18.6%), chest pain (16.4%), febrile neutropenia (16.4%), myalgia (15.9%), injection site reaction (13.6%), aggravated fatigue (12.7%) and malaise (10.9%).

Because treatment with Azacitidine is associated with neutropenia and thrombocytopenia, complete blood counts should be performed as needed to monitor response and toxicity, but at a minimum, prior to each dosing cycle.

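### Section 5.2 writes all four azacitidine count thresholds per dL, ten times the values that fit the rule, so the restart condition is wrong as written

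*Combined protocol and SAP*

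**What the plan says.** Section 5.2 (Trial Treatments) of the combined protocol and SAP sets one rule for lowering and restarting azacitidine after prolonged myelosuppression. It uses four count thresholds.

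- **Trigger.** The count part is "absolute neutrophil count of less than $1 \times 10^9/\text{dl}$ and a platelet count of less than $30 \times 10^9/\text{dL", lasting more than 42 days. A marrow condition is added: "with evidence of hypocellular marrow (defined as marrow cellularity of less than 5" (the figure is a percentage).
- **Consequence.** Once the trigger is met, "subsequent courses of the azacitidine will be given at the next lower dose after the counts have recovered".
- **Restart.** Recovery means counts that have "recovered to an ANC of more than $1 \times 10^9/\text{dL}$ and platelet more than $30 \times 10^9/\text{dL".

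The unit is a decilitre each time, written once as dl and three times as dL. Table 4 in Section 5.2.1.3 lists the reduced dose levels for Grade 3-4 hematological toxicity but gives no counts. The flow chart in Section 6.1 and the laboratory list in Table 6 give none either. Section 5.2 is therefore the only source for these thresholds.

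**The concern.** The rule governs when a cytotoxic drug may be given again, so its numbers are operative. Taken per decilitre, they contradict the condition they are meant to define. Section 4.1 describes MDS as "heterogeneous malignancies that manifest clinically by peripheral cytopenias", and Section 9.6 carries its own warning: "Because treatment with Azacitidine is associated with neutropenia and thrombocytopenia". A restart threshold far above what such a patient could be expected to reach after prolonged marrow suppression would in effect bar further azacitidine.

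Two practical points follow.

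- Footnote e to the Section 6.1 flow chart lets a patient's local physician give azacitidine and order routine laboratory tests after Cycle 1. The rule may therefore be applied away from the trial centre.
- A clinically sensible restart at, say, ANC 1.5 and platelets 50 x 10^9/L would breach the written text, so compliance with the rule cannot be audited cleanly.

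**Working it through.** No sample-size or probability calculation is involved. The check is a unit conversion, followed by a test of which reading fits the rule.

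**Inputs (all from Section 5.2)**

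- ANC threshold, trigger and restart: 1 x 10^9 per dL
- Platelet threshold, trigger and restart: 30 x 10^9 per dL
- Other parts of the trigger: more than 42 days, and marrow cellularity below 5%

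**Conversion**

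1 L = 10 dL = 10^6 uL. So the value per L is 10 x the value per dL, and the value per uL is the value per L divided by 10^6.

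| Threshold | As written | Literal, per L | Literal, per uL | If the unit were L, per uL | Ratio |
|---|---|---|---|---|---|
| ANC | 1 x 10^9/dL | 10 x 1 x 10^9 = 10 x 10^9/L | 10 x 10^9 / 10^6 = 10,000 | 1 x 10^9 / 10^6 = 1,000 | 10 |
| Platelets | 30 x 10^9/dL | 10 x 30 x 10^9 = 300 x 10^9/L | 300 x 10^9 / 10^6 = 300,000 | 30 x 10^9 / 10^6 = 30,000 | 10 |

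Each threshold is used twice, once to trigger and once to restart, so the factor of 10 applies in all four places.

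**Which reading fits**

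- *Trigger.* Literally, a patient with an ANC of 9,000/uL and platelets of 290,000/uL satisfies the count part of prolonged myelosuppression. The count criteria then screen out very little, and duration and cellularity do nearly all the work. Per litre, the count part needs an ANC below 1,000/uL and platelets below 30,000/uL, which matches the name of the condition.
- *Restart.* Literally, a patient who has had more than 42 days of low counts and a marrow below 5% cellularity must exceed 10,000/uL and 300,000/uL before the next course. Per litre, the patient must exceed 1,000/uL and 30,000/uL.

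**What the unit can and cannot do to the trigger**

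The unit alone cannot cause a dose reduction, because duration and cellularity must also be met. It can still decide the matter for a patient who meets both. Someone whose ANC is below 10 and platelets below 300 x 10^9/L, but who is not below both 1 and 30 x 10^9/L, meets the literal trigger and not the per-litre one.

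**The case against.** The strongest reply accepts the conversion and argues that this is a self-evident typing slip. The sentence names the state it defines, and no hematologist would call an ANC just under 10,000/uL myelosuppression, so the text largely exposes its own error. The restart clause also applies only to patients who meet every part of a demanding trigger. Others fall under different text: the first course is given whatever the degree of myelosuppression, and later intervals may be lengthened at the physician's discretion. Section 5.2.1.3 also allows further azacitidine adjustments on clinical grounds. The document does not estimate how many patients would meet the trigger. The neutropenia and thrombocytopenia frequencies in Section 9.6 (32.3% and 65.5%) come without grades or counts, so they cannot supply that estimate. Finally, per litre is an inference.

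Most of this stands as a limit on the practical effect. The restart condition matters only for the subset who meet the trigger, the size of that subset is unknown, and the Section 9.6 percentages say nothing about it. It does not make the text correct. The freedom to space cycles and adjust doses does not restate or override the recovery counts. A reader's ability to guess the right unit is no reason to leave the wrong one in a dosing rule.

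A text-extraction fault is an unlikely explanation, because the extra letter would have to appear four times and in two different cases.

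**Conclusion.** The concern holds. All four azacitidine count thresholds in Section 5.2 are wrong as written, by a factor of 10 if the intended unit is the litre. The literal values are 10 and 300 x 10^9/L, against 1 and 30 x 10^9/L. The main consequence is a restart condition that is unworkable for patients who meet the trigger. The secondary one is a trigger whose count criteria exclude very few patients.

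The conclusion rests on one assumption: that the litre was meant. The document does not say so, but the rule's stated purpose, its marrow criterion and the Grade 3-4 heading of Table 4 all point that way. The likely effect in practice is small, because experienced readers would probably correct the unit for themselves. The text should be corrected, but nothing in the sample size, the stopping boundaries or the response analysis changes.

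**What to change.** In Section 5.2, replace dl or dL with L in all four places. The trigger then reads ANC below 1 x 10^9/L and platelets below 30 x 10^9/L, and recovery reads ANC above 1 x 10^9/L and platelets above 30 x 10^9/L. The sponsor should confirm these values, since the intended unit is inferred. The cost is a short text correction at the next amendment, with no change to design or analysis.

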5.2.1 Dose Selection/Modification

5.2.1.1 Dose Selection

The rationale for selection of doses to be used in this trial is provided in Section 4.0 – Background and Rationale.

Details on preparation and administration of pembrolizumab (MK-3475) are provided in the Pharmacy Manual.

We will use the standard dosing of Azacitidine.

5.2.1.2 Dose Modification of MK3475

Adverse events (both non-serious and serious) associated with pembrolizumab exposure may represent an immunologic etiology. These adverse events may occur shortly after the first dose or several months after the last dose of treatment. Pembrolizumab must be withheld for drug-related toxicities and severe or life-threatening AEs as per Table 3 below. See Section 5.6.1 for supportive care guidelines, including use of corticosteroids.

Table 3. Dose Modification Guidelines for Drug-Related Adverse Events

Toxicity	Hold Treatment For Grade	Timing for Restarting Treatment	Discontinue Subject
Diarrhea/ Colitis	2-3	Toxicity resolves to Grade 0-1	Toxicity does not resolve within 12 weeks of last dose or inability to reduce corticosteroid to 10 mg or less of prednisone or equivalent per day within 12 weeks.

Product: Pembrolizumab

Protocol/Amendment No.: 2016-0343 Amendment 3.4

Toxicity	Hold Treatment For Grade	Timing for Restarting Treatment	Discontinue Subject
	4	Permanently discontinue	Permanently discontinue
AST, ALT, or Increased Bilirubin	2	Toxicity resolves to Grade 0-1	Toxicity does not resolve within 12 weeks of last dose.
	3-4	Permanently discontinue (see exception below) ¹	Permanently discontinue
Type 1 diabetes mellitus (if new onset) or Hyperglycemia	T1DM or 3-4	Hold pembrolizumab for new onset Type 1 diabetes mellitus or Grade 3-4 hyperglycemia associated with evidence of beta cell failure.	Resume pembrolizumab when patients are clinically and metabolically stable.
Hypophysitis	2-3	Toxicity resolves to Grade 0-1	Toxicity does not resolve within 12 weeks of last dose or inability to reduce corticosteroid to 10 mg or less of prednisone or equivalent per day within 12 weeks.
	4	Permanently discontinue NOTE: Grade 4 hypophysitis does not require stopping therapy with pembrolizumab as long as the pituitary hormones are replaced.	Permanently discontinue NOTE: Grade 4 hypophysitis does not require stopping therapy with pembrolizumab as long as the pituitary hormones are replaced.
Hyperthyroidism	3	Toxicity resolves to Grade 0-1	Toxicity does not resolve within 12 weeks of last dose or inability to reduce corticosteroid to 10 mg or less of prednisone or equivalent per day within 12 weeks.
	4	Permanently discontinue	Permanently discontinue
Hypothyroidism	2-4	Therapy with pembrolizumab can be continued while treatment for the thyroid disorder is instituted	Therapy with pembrolizumab can be continued while treatment for the thyroid disorder is instituted.
Infusion Reaction	3-4	Permanently discontinue	Permanently discontinue
Pneumonitis	2	Toxicity resolves to Grade 0-1	Toxicity does not resolve within 12 weeks of last dose or inability to reduce corticosteroid to 10 mg or less of prednisone or equivalent per day within 12 weeks.
	3-4	Permanently discontinue	Permanently discontinue

Toxicity	Hold Treatment For Grade	Timing for Restarting Treatment	Discontinue Subject
Renal Failure or Nephritis	2	Toxicity resolves to Grade 0-1	Toxicity does not resolve within 12 weeks of last dose or inability to reduce corticosteroid to 10 mg or less of prednisone or equivalent per day within 12 weeks.
	3-4	Permanently discontinue	Permanently discontinue
All Other Drug-Related Toxicity ²	3 or Severe	Toxicity resolves to Grade 0-1	Toxicity does not resolve within 12 weeks of last dose or inability to reduce corticosteroid to 10 mg or less of prednisone or equivalent per day within 12 weeks.
	4	Permanently discontinue	Permanently discontinue

Note: Permanently discontinue for any severe or Grade 3 drug-related AE that recurs or any life-threatening event.

¹ For patients with liver metastasis who begin treatment with Grade 2 AST or ALT, if AST or ALT increases by greater than or equal to 50% relative to baseline and lasts for at least 1 week then patients should be discontinued.

² Patients with intolerable or persistent Grade 2 drug-related AE may hold study medication at physician discretion. Permanently discontinue study drug for persistent Grade 2 adverse reactions for which treatment with study drug has been held, that do not recover to Grade 0-1 within 12 weeks of the last dose.

Dosing interruptions are permitted in the case of medical / surgical events or logistical reasons not related to study therapy (e.g., elective surgery, unrelated medical events, patient vacation, and/or holidays). Subjects should be placed back on study therapy within 3 weeks of the scheduled interruption, unless otherwise discussed with the Sponsor. The reason for interruption should be documented in the patient's study record.

5.2.1.3 Dose Modification of azacitidine

Hematological toxicities will be attributed primarily to Azacitidine and preferentially will be dose reduced according to Table 4 below:

Table 4: Dose Adjustments for Grade 3 – 4 Hematological Toxicity

	Azacitidine IV/SC (x 7 days)
--	------------------------------

Product: Pembrolizumab

Protocol/Amendment No.: 2016-0343 Amendment 3.4

Level – 1	50 mg/m ² /day
Level – 2	25 mg/m ² /day

Further adjustments of azacitidine can be implemented as clinically indicated (i.e reducing to 5 days).

5.2.2 Timing of Dose Administration

Therapy can be administered in an outpatient or inpatient bases depending on clinical needs. Azacitidine will be administered on day 1 to 7. Therapy will be repeated every 4 weeks. MK3475 (Pembrolizumab) will be administered starting on Cycle 1 Day 1 and every 3 weeks thereafter. Azacitidine treatment should be administered on Day 1 of each cycle after all procedures/assessments have been completed as detailed on the Trial Flow Chart (Section 6.0). Trial treatment may be administered up to 3 days before or after the scheduled Day 1 of each cycle due to administrative reasons.

Pembrolizumab 200 mg will be administered as a 30 minute IV infusion every 3 weeks. Sites should make every effort to target infusion timing to be as close to 30 minutes as possible. However, given the variability of infusion pumps from site to site, a window of -5 minutes and +10 minutes is permitted (i.e., infusion time is 30 minutes: -5 min/+10 min).

The Pharmacy Manual contains specific instructions for the preparation of the pembrolizumab infusion fluid and administration of infusion solution.

Azacitidine will be administered using standard guidelines.

5.2.3 Trial Blinding/Masking

This is an open-label trial; therefore, the Sponsor, investigator and subject will know the treatment administered.

5.3 Randomization or Treatment Allocation

This is not a randomized trial. Patients will be allocated based on their disease status.

5.4 Stratification

There is no stratification on this trial. Patients will be allocated based on their disease status.

5.5 Concomitant Medications/Vaccinations (allowed & prohibited)

Medications or vaccinations specifically prohibited in the exclusion criteria are not allowed during the ongoing trial. If there is a clinical indication for one of these or other medications or vaccinations specifically prohibited during the trial, discontinuation from trial therapy or

Product: Pembrolizumab

Protocol/Amendment No.: 2016-0343 Amendment 3.4

vaccination may be required. The investigator should discuss any questions regarding this with the Merck Clinical team. The final decision on any supportive therapy or vaccination rests with the investigator and/or the subject's primary physician.

5.5.1 Acceptable Concomitant Medications

All treatments that the investigator considers necessary for a subject's welfare may be administered at the discretion of the investigator in keeping with the community standards of medical care. All concomitant medication will be recorded on PDMS/CORe including all prescription, over-the-counter (OTC), herbal supplements, and IV medications and fluids. If changes occur during the trial period, documentation of drug dosage, frequency, route, and date may also be included on the CRF.

- The protocol specific data will be entered into PDMS/CORe, the electronic case report form.
- The Investigator or physician designee is responsible for providing source documentation and assigning attribution for all AEs.

All concomitant medications received within 28 days before the first dose of trial treatment and 30 days after the last dose of trial treatment should be recorded. Concomitant medications administered after 30 days after the last dose of trial treatment should be recorded for SAEs as defined in Section 7.2.

5.5.2 Prohibited Concomitant Medications

Subjects are prohibited from receiving the following therapies during the Screening and Treatment Phase (including retreatment for post-complete response relapse) of this trial:

- Antineoplastic systemic chemotherapy or biological therapy
- Immunotherapy not specified in this protocol
- Chemotherapy not specified in this protocol
- Investigational agents other than pembrolizumab
- Radiation therapy
 - Note: Radiation therapy to a symptomatic solitary lesion or to the brain may be allowed at the investigator's discretion.
- Live vaccines within 30 days prior to the first dose of trial treatment and while participating in the trial. Examples of live vaccines include, but are not limited to, the following: measles, mumps, rubella, varicella/zoster, yellow fever, rabies, BCG, and typhoid vaccine.

Product: Pembrolizumab

Protocol/Amendment No.: 2016-0343 Amendment 3.4

- Systemic glucocorticoids for any purpose other than to modulate symptoms from an event of clinical interest of suspected immunologic etiology. The use of physiologic doses of corticosteroids may be approved after consultation with the Sponsor.

Subjects who, in the assessment by the investigator, require the use of any of the aforementioned treatments for clinical management should be removed from the trial. Subjects may receive other medications that the investigator deems to be medically necessary.

The Exclusion Criteria describes other medications which are prohibited in this trial.

There are no prohibited therapies during the Post-Treatment Follow-up Phase.

